10.9.1. Adverse Events

All adverse events (AE) will be coded using MedDRA, Version 25.0.

An adverse event is defined as treatment emergent if the onset date is on or after the date of first dosing with IMP. Should any onset date for an adverse event be missing or only a partial date recorded (such that it cannot be determined if the event onset was prior to start of IMP or not) then it will be assumed that the event is treatment emergent, unless the adverse event stop date indicates otherwise.

Similarly, an AE is defined as challenge emergent if the onset date is on or after the date of inoculation. Should any onset date for an adverse event be missing or only a partial date recorded (such that it cannot be determined if the event onset was prior to inoculation or not) then it will be assumed that the event is challenge emergent, unless the adverse event stop date indicates otherwise.

An AE can be both challenge emergent and treatment emergent. Any AE with an onset date earlier than the inoculation date will be classified as a pre-treatment AE.

If a participant experiences more than one adverse event with the same preferred term, that preferred term will be counted only once. It will be assigned the greatest observed severity and the strongest relationship to IMP among those events for the tables in which those characteristics are summarised.

Pre-treatment AEs will be identified in a patient listing.

A summary of treatment-emergent AEs will be presented by treatment group showing the number of events, number of participants with events (also split by severity; mild, moderate, severe), number of participants with SAEs, number of participants with related events, number of participants with events

leading to early withdrawal from the study and the number of participants with events leading to early discontinuation of IMP.

Further summaries will present the treatment-emergent AEs by:

- Treatment group, SOC and PT.
- Treatment group, SOC, PT and severity.
- Treatment group, SOC, PT and relationship to IMP.

Further summaries will present the challenge-emergent AEs by:

- Treatment group, SOC, PT and relationship to challenge agent.

Tables presented by relationship will only include the subset of adverse events that are judged as being 'Related' to IMP or challenge agent, i.e. correspond to adverse events where relationship is recorded on the adverse event page as being 'Unlikely', 'Possibly', 'Probably', 'Definitely', or a relationship is not given.

In all AE summary tables results will be displayed ordered in terms of decreasing frequency of SOC occurrence (based on total across all participants), and within each SOC also ordered in terms of decreasing frequency of preferred term occurrence (also based on total across all participants). In all AE summary tables a total column including data across all participants will also be presented.

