	
 • HVC: 
 ○ RSV-A Memphis 37b virus inoculation on Day 0. • Post-HVC: 
 ○ Randomisation to receive RV299 or matched placebo. ○ Administration of IMP (RV299/placebo). Each participant will receive IMP twice daily (~12 hours interval) for 5 consecutive days: 
 ▪ IMP dosing to start on confirmation of RSV infection, i.e., after a positive result by qualitative integrative cycler polymerase chain reaction (qicPCR). The qicPCR of nasal wash will be performed twice daily on Days 2-5 (Day 5 morning only), or until a positive result is received, whichever is sooner. The earliest start of IMP dosing will be in the evening of Day 2 post-HVC (IMP will be initiated 12 hours \pm 1-hour post nasal wash confirmation of infection) ▪ OR ▪ IMP would start in the evening of Day 5, if no positive result obtained by qicPCR ○ Day 1 onwards and each day – study assessments will be conducted as per SoE. ○ Participants will be discharged from the quarantine unit on Day 12 (or may remain longer at the discretion of the principal investigator [PI]/investigator). - Outpatient phase: 
 • Final visit: Day 28 (\pm3 days).
Randomisation	1:1 to RV299 or matched placebo
Participant replacement policy	If a participant discontinues from study intervention OR withdraws from the study for reasons not related to AEs, a replacement participant may be enrolled if deemed appropriate by the PI/investigator and sponsor. The replacement participant will generally receive the same intervention as the participant being replaced. The replacement participant will be assigned a unique treatment/randomisation number.
Expected duration of participation per participant	Approximately 4 months from screening to the participant's last scheduled visit.
Overall duration of clinical phase	The length of the clinical phase is expected to be approximately 7 months from first participants planned first screening visit to the last participants last scheduled study visit.
End of study	The end of the study is defined as the date of the last visit of the last participant in the study.
CCI	

	
CCI
 
■

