6.4. Study Intervention Compliance

When participants are dosed at the site, they will receive study intervention and challenge agent directly from the PI/investigator or designee, under medical supervision. The date and time of each dose administered at the study site will be recorded in the source documents and recorded in the electronic case report form (eCRF). The dose of study intervention and study participant identification will be confirmed at the time of dosing by a member of the PI/investigator site staff other than the person administering the study intervention.

Any noncompliance or problems with the administration of the study intervention will be recorded in the participant's source notes and reported to the sponsor, if appropriate.

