10.3.6. Recording, Assessment, and Follow-up of Adverse Events/Serious Adverse Events

10.3.6.1. Adverse Event/Serious Adverse Event Recording

All AEs/SAEs will be collected from the time of written study-specific informed consent until study completion/final study contact or until the resolution of the AE. Adverse events will be fully recorded in the source documents as they are reported whether spontaneously reported by a participant or in response to questioning about wellbeing at each face-to-face study visit and during telephone calls. Enquiries about AEs should cover the period between the previous and current visit.

The following are examples of open-ended, non-leading questions that may be used to obtain this information:

- How are you feeling?
- Have you had any medical problems since your last visit/assessment?
- Have you taken any new medicines, other than those given to you in this study, since your last visit/assessment?

Following the reporting of AEs and concomitant medication, the PI/investigator should assess the participant's eligibility to continue in the study.

The PI/investigator will record all relevant information regarding an AE/SAE in the source documents and evaluate AEs/SAEs using the following guidelines:

- Description of event (if the event consists of a cluster of signs and symptoms, a diagnosis should be recorded)
- Seriousness
- Grade (or severity)
- Onset date and time
- Frequency

- Date and time of resolution (or 'continuing' if unresolved)
- Action taken
- Concomitant medication
- Clinical outcome
- Relationship or causality (IMP/challenge agent/study procedures/concomitant medication/other).

Any clinically significant abnormal laboratory result, vital sign or other measure will be followed until resolution (return to normal or baseline values), stabilisation, it is judged by the PI/investigator to be no longer clinically significant, the participant is lost to follow-up, or an alternative explanation has been provided.

If an AE is not resolved at the end of the study, the AE should be followed until it has resolved or (in the case of pregnancy) the pregnancy has been terminated (including spontaneous abortion), resulted in a birth, or a decision has been made by the sponsor that no further follow-up is required.

Even if the AE/SAE is assessed by the PI/investigator as not reasonably attributable to the challenge agent, its occurrence must be fully documented in the source notes.

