10.3.6.2. Assessment

Description

If the event consists of a cluster of signs and symptoms, a diagnosis should be recorded (e.g., gastroenteritis) rather than each sign and symptom.

Onset and end

The dates and times of the onset and end of the event should be recorded.

Assessment

Challenge Agent-related Symptoms
 
The PI/investigator will assess, and review challenge agent-related symptoms recorded in participants' hVIVO symptom diary cards. Symptoms greater than Grade 0 will be expected and presumed to represent infection consequent to challenge agent inoculation and will not be additionally captured as AEs unless they meet the definition of an AE and are deemed to be clinically significant (in the opinion of the PI/investigator).
 
Following challenge agent inoculation all unexpected (in the opinion of the PI/investigator) symptoms post inoculation will be captured as AEs, along with all other occurrences that meet the criteria for an AE.

Physical Examination
 
Any clinically significant change in complete physical examination findings during the study will be documented as an AE.

Symptom-directed Physical Examination

Following challenge agent inoculation, URT symptoms (nasal discharge, otitis, pharyngitis, sinus tenderness) and LRT symptoms (abnormal breath sounds externally [e.g., stridor, wheezing] and on chest auscultation [rhonchi, crepitations or other]) will be expected and presumed to represent infection consequent to challenge agent and will not be additionally captured as AEs unless they meet the definition of an AE and are deemed to be clinically significant (in the opinion of the PI/investigator).

Vital Signs

Deterioration in a vital sign (compared to baseline) should only be reported as an AE if the deterioration fulfils the criteria for an AE. If deterioration in a vital sign is associated with clinical signs and symptoms, the sign or symptom will be reported as an AE and the associated vital sign will be considered as additional information.

Temperature

Following challenge agent inoculation, pyrexia (temperature $\geq 37.9^{\circ}\text{C}$) will be expected and presumed to represent infection consequent to challenge agent and will not be additionally captured as an AE unless it meets the definition of an AE and is deemed to be clinically significant (in the opinion of the PI/investigator) to be classed as an AE.

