Data recorded for replaced participants will be listed. However, these participants will only be included in tables where they meets the inclusion criteria for the relevant population.

Within summary presentations/analyses it is envisaged that only scheduled protocol visit values will be used for post-baseline time points and unscheduled visits will not be summarised in tables. All unscheduled visits will be listed. However, at the BDRM the occurrence of such non-scheduled data will be reviewed for each participant to decide if (and how) any such data point(s) should be included within summary presentations/analyses. Any such decisions will be documented in the BDRM minutes.

For assessments made on Day 0 (either pre or post challenge), the date and time of inoculation will be compared to the date and time of assessment to ensure they are assigned to either pre or post challenge accurately.

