Note: If a participant experiences more than one event, then the event with the worst severity or strongest relationship is included in the relevant level of summarisation.

Note: Related = 'Unlikely', 'Possibly', 'Probably', 'Definitely' or 'Not assessed'.

Note: Adverse Event Leading to Discontinuation from the Study = Participant withdrew from the study due to an adverse event.

Note: Adverse Event Leading to Discontinuation of Dosing = Action taken of 'Trial/Study drug permanently discontinued'.

Note: Percentages are based on the safety population.

Table 14.3.1.68
 Treatment Emergent Adverse Events by System Organ Class and Preferred Term
 Safety Population

System Organ Class/ Preferred Term [1]	Treatment Group			
	RV299 (N=xx)	n (%)	Placebo (N=xxx)	n (%)
Number of Events	XX		XX	
Number of Subjects with any adverse event	XX	(XX.X)	XX	(XX.X)
System Organ Class 1	XX	(XX.X)	XX	(XX.X)
Preferred Term 1	XX	(XX.X)	XX	(XX.X)
Preferred Term 2	XX	(XX.X)	XX	(XX.X)
System Organ Class 2	XX	(XX.X)	XX	(XX.X)
Preferred Term 1	XX	(XX.X)	XX	(XX.X)
Preferred Term 2	XX	(XX.X)	XX	(XX.X)

[1] MedDRA Version 25.0.

Note: Treatment emergent events are those events with an onset on or after the first administration of IMP.

Note: Table shows distinct number of participants with events for each system organ class/preferred term.

Note: Percentages are based on the safety population.

Table 14.3.1.3
Treatment Emergent Adverse Events by System Organ Class, Preferred Term and Severity
Safety Population

System Organ Class/ Preferred Term [1]	Treatment Group			
	RV299 (N=xx)	n (%)	Placebo (N=xxx)	n (%)
System Organ Class 1				
Mild	XX	(XX.X)	XX	(XX.X)
Moderate	XX	(XX.X)	XX	(XX.X)
Severe	XX	(XX.X)	XX	(XX.X)
Preferred Term 1				
Mild	XX	(XX.X)	XX	(XX.X)
Moderate	XX	(XX.X)	XX	(XX.X)
Severe	XX	(XX.X)	XX	(XX.X)
Preferred Term 2				
Mild	XX	(XX.X)	XX	(XX.X)
Moderate	XX	(XX.X)	XX	(XX.X)
Severe	XX	(XX.X)	XX	(XX.X)
System Organ Class 2				
Mild	XX	(XX.X)	XX	(XX.X)
Moderate	XX	(XX.X)	XX	(XX.X)
Severe	XX	(XX.X)	XX	(XX.X)
Preferred Term 1				
Mild	XX	(XX.X)	XX	(XX.X)
Moderate	XX	(XX.X)	XX	(XX.X)
Severe	XX	(XX.X)	XX	(XX.X)

[1] MedDRA Version 25.0.

Note: Treatment emergent events are those events with an onset on or after the first administration of IMP.

Note: This table shows distinct number of participants with events for each system organ class/preferred term/severity. If a participant experienced a specific event more than once then the event with the worst severity is summarised.

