Treatment Group	Participant	Days from IMP administration to planned discharge	Sum Total Symptom Score (from IMP administration to planned discharge)	Peak Total Symptom Score (from IMP administration to planned discharge)	Peak Daily Total Symptom Score (from IMP administration to planned discharge)	Time to Symptom Resolution from IMP administration (days)	Time to Symptom Resolution from Peak Symptom after IMP administration (days)	Time to Peak Total Symptom Score from IMP administration (days)
xxxxxx	xxxxxx	XX	XX	XX	XX	XX	XX	XX

Note: Derivations made for 10-items of the 13-item diary card.

Programming Note: Place the endpoints that are not by study day onto the first row for each participant.

Listing 16.2.6.4.1
Mucus Weight and Tissue Bag Distribution

Treatment Group	Participant	Study Day	Date Collected	Tissue Bag Distribution		Tissues Taken	Total Tissues Taken	Mucus Weight (g)	Total Mucus Weight (g)	Comments
				Time Collected/Dispensed	hh:mm					
xxxxxx	xxxxxx	xx	ddmm/yyyy			xxxx	xxxx	xxxx	xxxx	

Programming note: The Total Mucus Weight and Total Tissues Taken will be listed against the Day 12 observation.

Listing 16.2.6.5.1
Nasopharyngeal Swab: Respiratory Virus Screen/Rapid Viral Antigen Test

Treatment Group	Participant	Sample Collection Date / Time (Study Day)	Result	Comments
xxxxxx	xxxxxx	ddmmyyyy / hh:mm (xx)	Positive / Negative	xxxxxxxx

Listing 16.2.6.6
Plasma PK Parameters

Treatment Group	Participant	Day	PK Parameter	Units	RV299	Comments
xxxxxx	xxxxxx	XXX	XXX	XXX	XXX	xxxxxxxx

Listing 16.2.7
Adverse Events

Treatment Group / Participant /AE Number	MedDRA SOC / Preferred Term [1] / Adverse event (verbatim)	Start Date Time (study day) / Stop Date Time (Study day)	TE [2] / CE [3] / Severity / Frequency [4]	SAE / Serious Criteria [5]	Outcome [6] / Action Taken IMP [7] / Action Taken [8] /	Related to [9] IMP / Challenge Agent / Concomitant medication / Procedure / Other	Comments
xxxxxx / xxxx / xx	xxxxxxxxx/xxxxxx/xxxxxx	ddmmmyyyy hh:mm (xx) / ddmmmyyyy hh:mm (xx)	Yes or No / (xx) / Yes or No / Mild, Moderate, Severe, Life- Threatening / xx	Yes or Blank / xx	x / x / x	x / x / x / x / x	xxxxxxxxxxxx xxxxxxxxxxxx

TE = Treatment Emergent. SAE = Serious Adverse Event.

[1] MedDRA Version 24.0.

[2] An AE occurring on or after the first administration of IMP.

[3] An AE occurring on or after the challenge agent inoculation.

[4] Freq = Frequency. For frequency categories, C = Continuous, I = Intermittent, S = Single Episode.

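### SAP 10.9.1 classes adverse events as treatment-emergent and challenge-emergent by calendar date although clock times are recorded, giving a small over-count of emergent events in both arms

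*SAP*

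**What the plan says.** **The rule.** SAP 10.9.1: "An adverse event is defined as treatment emergent if the onset date is on or after the date of first dosing with IMP". The same section treats an event as challenge-emergent when its onset date is the inoculation date or later. It keeps the pre-treatment label for onset dates earlier than the inoculation date. A missing or partial onset date that leaves the order unclear defaults to emergent, unless the stop date shows otherwise.

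**The endpoint.** Protocol Section 3 and SAP 7.2 count AEs and SAEs from the first IMP administration to Day 28, and challenge-related events from the viral challenge.

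**The shells.** Notes under the AE tables in SAP Section 14 read "Treatment emergent events are those events with an onset on or after the first administration of IMP". They do not say whether date or time decides.

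**What is recorded.** Protocol 10.3.6.1 lists "Onset date and time" among the AE items, and 10.3.6.2 adds "The dates and times of the onset and end of the event should be recorded". Listing 16.2.7 shows the AE start date and time. For IMP, Protocol 6.4 says "The date and time of each dose administered at the study site will be recorded in the source documents", and the same goes into the eCRF. Protocol 6.2.2 requires the exact inoculation time to be logged.

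**When dosing starts.** The protocol synopsis says: "The earliest start of IMP dosing will be in the evening of Day 2 post-HVC". Participants with no positive qicPCR start in the evening of Day 5.

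**The concern.** The endpoint starts at a clock time and the derivation starts at midnight before it. A participant first dosed at, say, 20:00 on Day 5 with an AE that began at 07:00 that day has a treatment-emergent AE under SAP 10.9.1, although onset came 13 hours before any IMP.

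The same happens on Day 0. AEs are collected from study-specific consent, so an event that starts on Day 0 before inoculation becomes challenge-emergent instead of pre-treatment.

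What is at stake is the accuracy of the TEAE tables. An event that IMP cannot have caused adds to the counts. SAP 10.9.1 also gives repeated events with one preferred term the greatest severity and the strongest relationship among them, so a pre-dose episode can set the severity shown for that participant.

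SAP Section 11 lists six changes to the protocol's analysis, and an earlier opening of the AE window is not among them.

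**Working it through.** The plan gives no figure for this, so there is none to reproduce. The check asks how often first doses fall late in the day, and how much pre-dose time the date rule then admits.

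**1. First-dose slots.** The protocol synopsis schedules qicPCR twice daily on Days 2 to 4 and in the morning of Day 5, with IMP about 12 hours after the positive wash.

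| Positive wash | First dose |
|---|---|
| Day 2 am | Day 2 pm |
| Day 2 pm | Day 3 am |
| Day 3 am | Day 3 pm |
| Day 3 pm | Day 4 am |
| Day 4 am | Day 4 pm |
| Day 4 pm | Day 5 am |
| Day 5 am | Day 5 pm |

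Four of seven slots are evenings. Never-positive participants also start on Day 5 pm.

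**2. Participants starting in the evening.** Let p be the proportion qicPCR-positive and s the share of positives dosed in an evening. Evening share = (1 − p) + p × s. The documents do not give p. Protocol Table 2-1 puts the chance of infection at 65% to 85%, used here as a proxy. N = 80.

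- s = 0 (every positive dosed in a morning): 0.15 × 80 = 12 to 0.35 × 80 = 28.
- s = 4/7 (positives spread evenly over the slots): 0.15 + 0.85 × 4/7 = 0.636, or 50.9 of 80; 0.35 + 0.65 × 4/7 = 0.721, or 57.7 of 80.
- s = 1: all 80.

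So at least 12 to 28 participants start in an evening under the proxy, and about 51 to 58 if positives spread evenly.

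**3. Pre-dose time admitted.** Let h be the clock hour of the first dose on Day d. The date rule adds h hours to a true window of (28 − d) × 24 + 12 − h hours, ending at an assumed noon on Day 28. The documents give no clock times, so 08:00 and 18:00 to 22:00 are assumptions.

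| First dose | h | True window (h) | Added |
|---|---|---|---|
| Day 3, 08:00 | 8 | 604 | 1.3% |
| Day 5, 08:00 | 8 | 556 | 1.4% |
| Day 2, 18:00 | 18 | 618 | 2.9% |
| Day 2, 20:00 | 20 | 616 | 3.2% |
| Day 5, 20:00 | 20 | 544 | 3.7% |
| Day 5, 22:00 | 22 | 542 | 4.1% |

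Under a date-and-time rule h is zero in every row.

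**4. Day 0.** The hours wrongly admitted equal the clock hour of inoculation, which the documents do not state, so no figure is given.

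**5. From hours to events.** The documents give no AE rate, no pattern of onset over the day and no distribution of first-dose slots. The percentages are shares of time. They do not convert to a number of AEs.

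**The case against.** The best defence is that dates are a deliberate, conservative convention. SAP 10.5 classes medications without using times, SAP 10.1.5 completes other partial dates conservatively, and over-inclusion cannot hide an event that IMP caused. That argument works where timing is unknown. It does not justify counting an event whose recorded time shows that it came first. SAP 10.5 says outright that times are not used; SAP 10.9.1 makes no such statement for AEs.

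SAP 10.1.1 sorts Day 0 data by clock: "the date and time of inoculation will be compared to the date and time of assessment". It can fairly be said that this concerns assessments and not AEs. It shows that the method is already in use but is not a competing AE rule. The table notes can likewise be read as shorthand for 10.9.1, so they need aligning; they do not prove a contradiction.

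The objections to a larger effect stand:

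- Protocol 10.3.1 and 10.3.6.2 keep most expected challenge symptoms out of AE reporting unless they are clinically significant. The Day 5 default starters have no positive qicPCR, so illness from the challenge is least expected in them.
- Protocol 10.3.6.5 makes the investigator weigh timing when judging causality. A pre-dose event would naturally be rated not related, and SAP 10.9.1 leaves such events out of the relationship tables. The only challenge-emergent summary is also by relationship, so the same filter applies to Day 0 events.
- The AE and dosing listings show dates and times, so every affected event can be found.

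A reader might infer that the rule distorts the comparison between arms. The documents do not support that: the arms are randomised 1:1 and blinded, the rule is the same in both, and SAP 10.9 makes safety descriptive only.

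A reader might also measure the extra hours against the inpatient stay. A 20:00 dose gives 20/228 = 8.8% for Day 2 and 20/156 = 12.8% for Day 5, counting to 08:00 on Day 12. The TEAE tables run to Day 28, so those figures overstate the effect on them.

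**Conclusion.** The concern holds in a limited form. As written, SAP 10.9.1 counts some events as treatment-emergent or challenge-emergent although their recorded times place them before the first dose or before inoculation. That departs from the stated endpoint.

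The effect is a small over-count in both arms, about 1% to 4% of the window to Day 28. It rests on the assumed dose times and a noon end on Day 28. The number of affected AEs cannot be derived. The misclassification is probably non-differential and is not shown to favour RV299 or placebo. It can raise TEAE counts and set a participant's worst severity for a preferred term. It does not touch the efficacy analyses or any hypothesis test.

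The correction is worth making before database lock because the data are already collected and the SAP leaves room for two programmers to produce different tables.

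**What to change.** In SAP 10.9.1:

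- Define treatment-emergent as onset date and time at or after the date and time of the first IMP dose.
- Define challenge-emergent as onset date and time at or after inoculation.
- Class AEs with onset on Day 0 before inoculation as pre-treatment.
- Where the onset date equals the dosing or inoculation date and the onset time is missing, count the event as emergent. For events with a known onset date, use that default nowhere else. The existing rule for missing or partial dates can stay.

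Use the same wording in the notes to the AE tables and Listing 16.2.7.

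The cost is a short SAP edit and a changed comparison in the derivation of the two flags. No new data, protocol procedure or site work is needed.
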